#### **5.4.1.** Screening and Treatment

During the screening period (up to 2 weeks) the patient's eligibility for trial participation will be evaluated.

All eligible patients will be randomized to receive IV infusions of either efgartigimed 10 mg/kg body weight or matching placebo throughout the trial.

All patients will initially receive weekly IV infusions from visits 1 to 4.

argenx BVBA Confidential Page 56 of 162

Based on the platelet counts as of visit 2, the dosing frequency can be altered from visits 5 to 16 according to the following rules (the change in dosing frequency will occur at the current visit):

- Reduce from weekly to q2w in patients achieving platelet counts of  $\geq 100 \times 10^9$ /L for 3 out of 4 consecutive visits (the fourth visit being the current visit), and have a platelet count of  $\geq 100 \times 10^9$ /L at the last of these 4 visits
  - -OR-
  - 3 consecutive visits
- Increase from q2w to weekly in patients whose platelet counts drop below 100×10^9/L on 2 consecutive visits
  - -OR-
  - $<30\times10^9/L$  at 1 visit
  - -OR-

in patients who receive rescue therapy (see Section 6.8.4)

- Temporary withholding treatment
  - o for reasons described in Section 4.5, IMP should be reintroduced once the investigator considers the undue risk to the patient has passed
  - o in patients with platelet counts greater than  $400 \times 10^9$ /L, IMP should be resumed at the 10 mg/kg q2w dose when the platelet count falls to fewer than  $150 \times 10^9$ /L
- Post-baseline platelet count can be performed within 1 day of the next procedure as per the SoA (both dosing and non-dosing visit), allowing the results to be incorporated into the criteria above.

From visits 17 to 24, the dosing frequency is fixed for each individual patient (ie, either weekly or q2w regimen), based on the regimen the patient was receiving at visit 16 or at the last visit at which IMP was administered.

Exceptions to the fixed dosing frequency are:

- Continued weekly dosing for patients requiring rescue therapy
- Continued q2w dosing for patients resuming IMP when the platelet count falls to fewer than 150×10^9/L after having had platelet counts greater than 400×10^9/L

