3.6.2 Derivation rules

The following parameters will be derived:

- Number of administrations: sum of all administrations of study drug.
- Compliance (%): 100*(number of doses received/number of doses expected); Compliance will be calculated over the 24-week treatment period and will take into account the weekly or q2w administration.

Notes:

- Dosing is expected at a visit except if reason not done is "DUE TO BIWEEKLY ADMINISTRATION" or "DUE TO PLATELET COUNT > 400X10^9/L"
- Only visits up to treatment discontinuation are considered in the compliance calculation.
- Cumulative duration of q2w dosing: number of weeks for which the patient was on the q2w dosing regimen
- Dosing frequency will be derived for subjects still being dosed at or after visit 17, based on dosing at CRF visits 14, 15, 16 and 17:
 - Biweekly (q2w): if the patient was not dosed at visit 15 or at visit 16
 "DUE TO BIWEEKLY ADMINISTRATION"
 - Else, Weekly: if the patient was dosed at both visit 15 and 16
 Note: in case of missing information at visit 15 and/or 16, a missed visit 15 or 16 is considered as dosed and visits 14 and 17 are also

SGS	Statistical Analysis Plan	
 ARGX-113-1801	Final analysis	Final 1.0 of 28MAR2022

taken into account. If the patient was dosed at two subsequent visits in this timeframe, dosing frequency is set to weekly.

• Else, Unknown: in case dosing frequency cannot be determined based on the above rules.

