4.2.2 Derivation rules

The following parameters from the individual serum drug concentration versus time profile for efgartigimod:

- C_{max}: maximum observed serum concentration
- C_{trough}: Serum concentration observed pre-dose

Concentration data-points with deviations outside the permitted time window (see section 4.2.1) will be excluded for the PK parameter derivation. C_{trough} will not be calculated at baseline and if the post-dose sample is missing, C_{max} will not be estimated.

4.2.3 **Presentation of results**

For tables by dosing frequency, only visits of the fixed dosing schedule period (i.e. baseline up to week 3 and week 16 up to week 24) will be tabulated. In this first period of baseline up to week 3, all patients have weekly dosing per protocol. For the second period, the dosing frequency is defined as explained in section 3.6.2.

SGS	Statistical Analysis Plan	
ARGX-113-1801	Final analysis	Final 1.0 of 28MAR2022

Individual concentration data and actual blood sampling times from start of IV infusion for PK assessments will be listed. Data issues like time deviations will be mentioned in the remarks.

Descriptive statistics on concentration data will be presented in tables per visit (and dosing frequency (weekly or q2w)) and per time point. A similar table will be created by ADA and by NAb Patient Classification.

Individual PK parameters will be listed.

Descriptive statistics on PK parameters will be presented in tables per visit (and dosing frequency (weekly of q2w)).

4.3 **PHARMACODYNAMICS**

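### SAP 3.6.2 sets one dosing-frequency label from visits 15 and 16 and carries it to week 24, so patients who change regimen around or after visit 16 can be tabulated under the wrong regimen

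*SAP*

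**What the plan says.** SAP 3.6.2 derives dosing frequency for patients still being dosed at or after visit 17, "based on dosing at CRF visits 14, 15, 16 and 17". The tests run in a fixed order. The first assigns q2w "if the patient was not dosed at visit 15 or at visit 16", where the recorded reason must be biweekly administration. The second is "Else, Weekly: if the patient was dosed at both visit 15 and 16". Whatever remains is Unknown. Visits 14 and 17 enter only through a note that begins "in case of missing information at visit 15 and/or 16, a missed visit 15 or 16 is considered as dosed and visits 14 and 17". That note ends by setting the label to weekly when two consecutive visits in the window were dosed. Nothing after visit 17 is used. SAP 3.6.2 also treats a dose not given because of a platelet count above 400×10⁹/L as a separate reason from a biweekly skip.

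SAP 4.2.3 (pharmacokinetics) and 4.3.3 (total IgG) tabulate weeks 16 to 24 by this label: "For the second period, the dosing frequency is defined as explained in section 3.6.2". SAP 3.6.3 reports it as the regimen over weeks 17 to 24. SAP 4.1.4 uses it as a subgroup factor for sustained platelet response.

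Protocol 5.4.1 lets frequency change up to and including visit 16, and "the change in dosing frequency will occur at the current visit". Visits 17 to 24 then follow the regimen in force at visit 16 or at the last dosed visit, with two listed exceptions. One is "Continued weekly dosing for patients requiring rescue therapy"; the other is q2w dosing on resumption after a count above 400×10⁹/L. Protocol 6.8.4 adds that q2w patients who are rescued move to weekly.

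**The concern.** The label stands for the regimen a patient was on during visits 17 to 24, but it is read mainly from visits 15 and 16. It does not use the direction of a change made at visit 16, and it takes no account of either protocol exception. A patient can therefore be dosed on one regimen and tabulated under the other.

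At stake are the weekly and q2w columns for concentrations, Cmax, Ctrough and total IgG in the fixed-schedule period, the exposure summary, and one efficacy subgroup factor. A reader would use these columns to compare exposure and IgG reduction between the two regimens.

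**Working it through.** This is a classification rule, so the check is to apply it to dosing patterns that the protocol permits. Codes: D dosed; B not dosed, biweekly; P held for a count above 400×10⁹/L; O withheld for another reason. The last column shows the label if the sentence on two consecutive dosed visits is read as a general override instead of as part of the missing-information note.

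| Situation | Visits 14/15/16/17 | Regimen under protocol | SAP as written | With override |
|---|---|---|---|---|
| Stable q2w | D/B/D/B or B/D/B/D | q2w | q2w | q2w |
| Stable weekly | D/D/D/D | weekly | Weekly | Weekly |
| A. q2w, visit 15 skipped, to weekly at visit 16 | D/B/D/D | weekly | **q2w** | Weekly |
| A′. q2w, visit 14 skipped, to weekly at visit 16 | B/D/D/D | weekly | Weekly | Weekly |
| B. q2w, rescue at visit 17 | B/D/B/D | weekly from rescue | **q2w** | **q2w** |
| B. q2w, rescue at visit 18 | D/B/D/B | weekly from rescue | **q2w** | **q2w** |
| C. Held at 15 and 16, resumed at 17 | D/P/P/D | q2w | **Unknown** | **Unknown** |
| C. Held at 15, resumed at 16 | D/P/D/B | q2w | **Unknown** | **Unknown** |
| C. Held at 14 and 15, resumed at 16 | P/P/D/B | q2w | **Unknown** | **Unknown** |
| C. Held at 16, resumed at 17 | D/D/P/D | q2w | **Unknown** | **Weekly** |
| D. Weekly, held at 17, resumed at 18 | D/D/D/P | q2w from resumption | **Weekly** | **Weekly** |
| D. Weekly, held at 18, then resumed | D/D/D/D | q2w from resumption | **Weekly** | **Weekly** |
| E. Weekly, dose withheld at 16 for IVIg or anti-D rescue | D/D/O/D | weekly | **Unknown** | Weekly |

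Cases A and A′ differ only in whether the q2w schedule fell on even or odd visits. In A the visit 16 dose was due anyway, so the switch first shows at visit 17, which the as-written rule does not consult.

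Doses at visits 17 to 24: there are 24 − 17 + 1 = 8 visits. A stable q2w patient receives 8 / 2 = 4 doses; case A receives 8. Case B with rescue at visit 18 skips visit 17 and is dosed at visits 18 to 24, which is 7 of 8, or 6 of 8 if IVIg or anti-D causes the visit 18 dose to be withheld.

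Rows affected: SAP 2.2.4 makes visit 2 week 1, so week 16 is visit 17, week 23 is visit 24, and week 24 is the End-of-Treatment visit. In case A the first row, week 16, already follows a 7-day interval (visit 16 to visit 17) yet sits in the q2w column. The schedule of assessments takes pharmacokinetic and IgG samples in this period only at infusion visits. A stable q2w patient therefore appears in 4 of the 8 visit rows, and a case A patient in all 8.

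Case C labels depend on the recorded reason. If the site enters the biweekly reason at visit 15 or 16, the q2w test is met and the label is right. Otherwise the hold reason cannot trigger that test.

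Reach: the label enters no primary, key secondary or safety analysis. SAP 4.1.4 excludes dosing frequency from the subgroups for extent of disease control, although the table list in SAP 8.1 includes such a table (14.2.2.6.3). If produced, it would carry the same label.

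**The case against.** The strongest reply concerns case A. If the sentence on two consecutive dosed visits applies generally, a patient dosed at visits 16 and 17 is Weekly, which is correct. The sentence sits inside the missing-information note, so the narrower reading is more natural, but the text permits both. The override repairs A and E only: B, D and three of the four C patterns are unchanged, and the fourth moves from Unknown to Weekly, which is also wrong.

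A second reply is that this is a landmark label, matching the protocol's anchor at visit 16. That has some force for B and D, where rows before the change are correctly labelled. It does not rescue the rule. Cases A and C miss the regimen at the landmark itself, and the SAP applies the label to every row through week 24 and describes it as the regimen over that period.

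It is also fair that Unknown is an open residual category and not a false assignment, that SAP 4.2.1 already drops pharmacokinetic samples between a missed dose and the next one, and that some patterns need a change at one particular visit.

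Three stronger readings are tempting and are not supported.

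- A reader might infer that these tables are the trial's only account of q2w exposure. Administrations, individual concentrations with sampling times, and IgG values are all listed. Cumulative time on q2w is summarised, and total IgG is also summarised overall.
- A reader might infer that q2w results will look more like weekly ones. A and B could act that way. C removes q2w patients with unknown effect, and D alters the weekly column.
- A reader might attach a percentage. With at most about 2/3 × (117 + 39) = 104 efgartigimod patients, supposing 20% on q2w gives about 21, and two misplaced patients would be about 10% of that column. Neither the 20% nor the two comes from the documents.

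**Conclusion.** The rule is wrong as written. It labels as q2w a patient who skipped visit 15 as biweekly and switched to weekly at visit 16, unless the consecutive-visits sentence is a general override. It also labels as q2w a q2w patient moved to weekly by rescue during visits 17 to 24. It labels as Unknown most patients held for a high count at visit 15 or 16 and resumed at q2w, and as Weekly those held at visit 17 or later and resumed at q2w.

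The consequence is limited to descriptive by-regimen tables, the exposure summary and one subgroup factor outside alpha control. The number of patients affected and the net direction of any bias cannot be determined from the documents. The conclusion rests on reading the SAP tests in their printed order and on holds being recorded under their own reason. It takes no view on which dosing rule is right.

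**What to change.** Reconcile SAP 3.6.2 with protocol 5.4.1 and 6.8.4:

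- For the pharmacokinetic and total IgG rows, derive the regimen visit by visit over visits 17 to 24 from recorded administration dates and not-done reasons.
- Where one patient-level label is needed, as for the efficacy subgroup, use the regimen in force at visit 17 after any change made at visit 16.
- Class patients resumed after a hold for a count above 400×10⁹/L by the regimen on resumption.
- State whether the sentence on two consecutive dosed visits applies only when information is missing.
- Show patients who change regimen during visits 17 to 24 separately.

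The derivation should not rely on the randomization system for a per-visit regimen, because the documents do not show that it holds one. The dates and reasons are already collected, so the cost is SAP wording and reprogramming one derived variable. No protocol amendment is needed.

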3.6.3 Presentation of results

Overall number of administrations, compliance, cumulative duration of q2w dosing and dosing regimen between week 17 and 24 will be summarized using descriptive statistics.

All study drug administration data will be listed.

4. EFFICACY, PHARMACOKINETIC, PHARMACODYNAMIC AND IMMUNOGENICITY ANALYSES

4.1 EFFICACY

4.1.1 Available data

Efficacy assessments will be assessed using platelet count, WHO-classified bleeding events, PROs (FACIT-Fatigue, FACT-Th6), QoL (SF-36),

, and

4.1.2 Endpoints and derivation rules

All efficacy endpoints will be analyzed on the overall FAS population or a subset of patients in the FAS with chronic ITP. For all references to weeks, analysis visits are considered as described in section 2.2.4 unless specified otherwise. If multiple assessments fall within the same analysis window, only the assessment closest to the target date will be considered unless specified otherwise. Other assessments within this window will only be listed and not considered in the below analyses. Only the time to response endpoint (see section 4.1.2.3) will be derived using all possible measurements and not only the one closest to the target of the analysis visit. Only visits during the treatment phase will be considered defining the different responses and time to response parameters.

4.1.2.1 PRIMARY ENDPOINT

The primary endpoint is the proportion of patients with a sustained platelet count response (week 19 - 24) within the adult population with chronic ITP.

A patient is considered a responder, i.e. has a sustained platelet count response, if he/she shows platelet counts of at least 50×10^9 /L for at least 4 of the 6 analysis visits between weeks 19 and 24 of the study. ($\geq 50 \times 10^9$ /L prim resp).

The main analysis on the primary endpoint will use the 'composite variable strategy' in case of main intercurrent events using the Cochran-Mantel-Haenszel test (see also section 4.1.3.2). This strategy implies that when a main intercurrent event occurs, a patient is considered a non-responder, if the patient has not achieved sustained platelet count response before the occurrence of the main intercurrent event. This happens in the following situations:

- early discontinuation of treatment (prior to week 24) due to lack of efficacy (DSDECOD = "Lack of efficacy") or due to an AE
- initiation of rescue therapy at week 12 or later: relative day of start date of rescue medication ≥ target ADY of analysis visit corresponding to Week 12

SGS	Statistical Analysis Plan	
ARGX-113-1801	Final analysis	Final 1.0 of 28MAR2022

- increase of dose and/or frequency of concurrent ITP therapies or start of a new concurrent ITP therapy at week 12 or later:
 - (if start date concurrent ITP therapy ≥ target ADY of analysis visit corresponding to Week 12) and (dose > previous dose of the specific ITP therapy OR frequency > previous frequency of the specific ITP therapy)

AND

(if start date concurrent ITP therapy ≥ target ADY of analysis visit corresponding to Week 12) and (dose > dose of the specific ITP therapy at baseline OR frequency > frequency of the specific ITP therapy at baseline)

OR

• new ITP therapy

Note: if for frequency a change is detected, but it is not clear whether a real increase has taken place, it will be considered worse-case and analysed as increase (e.g.: Baseline value 'QD' changed to e.g. 'at will', 'as needed'; Baseline value 'As needed' changed to e.g. 'QD, ', 'continuous').

Missing values for reasons other than the main intercurrent events, will be imputed as described in section 4.1.2.5 (approach 1).

A complementary analysis for this primary analysis will use the 'treatment policy strategy' where these main intercurrent events are handled differently.

The occurrence of the intercurrent event is irrelevant: the values for the platelet counts are used regardless of whether or not the intercurrent event occurs. For this strategy the data will be used as is, without taking into account intercurrent events. Missing values for reasons other than the main intercurrent events, will be imputed as described in section 4.1.2.5 (approach 1).

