### 3. TRIAL ENDPOINTS

# 3.1. Primary Endpoint

• Proportion of patients with chronic ITP with a sustained platelet count response defined as achieving platelet counts of at least 50×10^9/L for at least 4 of the 6 visits between week 19 and 24 of the trial.

Patients who discontinue treatment prior to visit 24 due to lack of efficacy (eg, more than 3 occurrences of rescue therapy) or due to an AE, and who have not achieved sustained platelet count response between week 19 and 24, are considered non-responders. Patients who receive rescue therapy at week 12 or later, or for whom dose and/or frequency of concurrent ITP therapies have increased at week 12 or later, are also considered non-responders.

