# Handling of main intercurrent events

A composite strategy approach will be taken to address the main intercurrent events described above. This implies that patients who discontinue treatment prior to visit 24 due to lack of efficacy (eg, more than 3 occurrences of rescue therapy) or due to an AE, as well as patients who receive rescue therapy at week 12 or later, or for whom dose and/or frequency of concurrent ITP therapies have increased at week 12 or later, will be considered non-responders for the primary endpoint analysis.

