1.2 STUDY ENDPOINTS

1.2.1 Primary endpoint

The primary endpoint is the proportion of patients with chronic ITP with a sustained platelet count response defined as achieving platelet counts of at least 50×10^9 /L for at least 4 of the 6 visits between week 19 and 24 of the study.

Patients who discontinue treatment prior to visit 24 due to lack of efficacy (e.g. more than 3 occurrences of rescue therapy) or due to an AE, and who have not achieved sustained platelet count response between week 19 and 24, are considered non-responders. Patients who receive rescue therapy at week 12 or later, or for whom dose and/or frequency of concurrent ITP therapies have increased at week 12 or later, are also considered non-responders.

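### The SAP keeps a patient as a primary responder after late rescue or a concurrent-therapy increase if response came first; the protocol makes every such patient a non-responder

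*SAP*

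**What the plan says.** Protocol 3.1 handles the events in two sentences. The first covers patients who stop treatment before visit 24 for lack of efficacy or an adverse event; those "and who have not achieved sustained platelet count response between week 19 and 24, are considered non-responders". The second begins "Patients who receive rescue therapy at week 12 or later, or for whom dose and/or frequency of concurrent ITP therapies have increased" and classes these patients as non-responders with no reference to earlier response. The synopsis and protocol 4.2 say the same, and SAP 1.2.1 repeats it: "increased at week 12 or later, are also considered non-responders".

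Protocol 8.4.1, under the handling of intercurrent events, lists patients who discontinue, "as well as patients who receive rescue therapy at week 12 or later", and patients with increased concurrent therapy. It says that all of them "will be considered non-responders for the primary endpoint analysis". It contains no exemption for any event.

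SAP 4.1.2.1, which defines the derivation for the main analysis, states that "a patient is considered a non-responder, if the patient has not achieved sustained platelet count response before the occurrence of the main intercurrent event". Beneath that condition it lists discontinuation, then "initiation of rescue therapy at week 12 or later: relative day of start date of rescue medication" (on or after the week 12 target day), then "increase of dose and/or frequency of concurrent ITP therapies or start of a new concurrent ITP therapy at week 12 or later".

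SAP 4.1.2.2 applies the same composite strategy to key secondary endpoint 2 (sustained response in the overall population) and endpoint 4 (6 of 8 visits, weeks 17 to 24). SAP 6.1, the list of changes from the protocol, does not mention it.

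**The concern.** This endpoint gates the whole testing hierarchy, and the documents disagree on who is a responder. Take a patient with counts of at least 50×10⁹/L at weeks 19 to 22 who then falls below 30×10⁹/L, bleeds and is rescued in week 23. SAP 4.1.2.1 calls this a sustained response; protocol 3.1, protocol 8.4.1 and SAP 1.2.1 call it a failure.

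For rescue and therapy increase, the SAP rule can only add responders relative to the protocol. The SAP also conflicts with itself. SAP 1.8 requires independent programming of the primary endpoint, and two programmers working from SAP 1.2.1 and SAP 4.1.2.1 could derive different flags.

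**Working it through.** **1. The rules side by side** (event at week 12 or later for rescue and therapy increase; before the end of treatment for discontinuation)

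| Source | Discontinuation (lack of efficacy or AE) | Rescue | Concurrent therapy increased |
|---|---|---|---|
| Protocol 3.1, synopsis, 4.2; SAP 1.2.1 | Failure unless response achieved | Failure | Failure |
| Protocol 8.4.1 | Failure | Failure | Failure |
| SAP 4.1.2.1 | Failure unless response came first | Failure unless response came first | Failure unless response came first |

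**2. When the rules can differ.** SAP 2.2.4 sets the target day of week w at 1 + 7w: week 12 = 85, week 19 = 134, week 22 = 155, week 24 = 169. Four qualifying counts from week 19 onward cannot be complete before week 22. On target days, the disputed interval is 169 − 155 = 14 days, out of 169 − 85 = 84 days from week 12 to week 24.

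**3. Which count patterns differ.** Each of the six visits is either at or above 50×10⁹/L or below it, giving 2⁶ = 64 patterns. For a patient with rescue or a therapy increase, the number of patterns still counted as response under SAP 4.1.2.1 is:

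- event just after week 21 or earlier: 0
- just after week 22: C(4,4) × 2² = 4
- just after week 23: [C(5,4) + C(5,5)] × 2 = 6 × 2 = 12
- just after week 24 (limiting case): C(6,4) + C(6,5) + C(6,6) = 15 + 6 + 1 = 22

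Under the protocol the number is 0 throughout. These are counts of patterns, not probabilities.

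**4. Effect of one patient on the test.** N = 117 at 2:1 gives 78 and 39. The planned N cannot be reproduced because both response rates are redacted, so the responder counts below are illustrative. The unstratified Mantel-Haenszel statistic, for a responders on efgartigimod and m in total, is (a − E)²/V, with E = 78m/117 and V = 78 × 39 × m(117 − m)/(117² × 116).

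| Responders | E | V | χ² | p |
|---|---|---|---|---|
| 15 vs 2 | 11.333 | 3.257 | 4.128 | 0.042 |
| 14 vs 2 | 10.667 | 3.096 | 3.589 | 0.058 |
| 18 vs 3 | 14.000 | 3.862 | 4.143 | 0.042 |
| 17 vs 3 | 13.333 | 3.716 | 3.618 | 0.057 |

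**5. Effect on power.** Assume placebo rates of 2% to 20%, each paired with the efgartigimod rate that just gives 90% power at 78:39 (22.8% to 49.8%). Lowering the expected efgartigimod responders by 1, 2 or 3 takes power from about 90% to about 87%, 83–84% or 78–81%.

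**6. Whether another planned analysis covers the protocol rule.** It does not. The complementary analysis is treatment policy and ignores the events. The sensitivity analyses change the imputation or use the per-protocol set. The exact logistic regression uses the same SAP 4.1.2.1 rule.

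**The case against.** The strongest reply is that the difference will rarely matter.

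- **Few routes remain.** Rescue needs a count below 30×10⁹/L plus bleeding, bleeding risk or urgent surgery. The permitted route for insufficient response needs no count of 30×10⁹/L or more in the last 4 weeks, so it is closed to a patient who has just had four counts of at least 50×10⁹/L among weeks 19 to 24. That leaves late rescue, label-based changes to oral TPO-RAs or fostamatinib, ambiguous frequency changes scored as increases, and deviations. This stands: the affected group is small, though not empty.
- **The p-values sit on a knife edge.** If the true rates were 15/78 vs 2/39 or 18/78 vs 3/39, the unstratified test would have only about 55% power, against the planned 90%. With 2 or 3 placebo responders, 90% power needs about 22 or 26 on efgartigimod. Losing one there matters little: 22 vs 2 gives p = 0.0037 and 21 vs 2 gives 0.0054; 26 vs 3 gives 0.0026 and 25 vs 3 gives 0.0037. The planned test is also stratified. This stands too: the borderline counts show sensitivity near the threshold and do not predict the result.
- **The direction is not fixed.** The exemption applies to both arms. If the patient losing status were on placebo, 15 vs 1 gives p = 0.014. This is correct.
- **The qualifying counts precede rescue, and the endpoint tolerates two failed visits.** This is true, and it could be argued as a reason for the SAP rule. But the protocol chose to make rescue itself a failure, and neither document gives a reason for departing from that.
- **The rule is openly stated in SAP 4.1.2.1, and intercurrent events will be tabulated and listed.** Disputed patients could therefore be found afterwards. That does not settle which rule is primary, and the rule is nowhere identified as a change.

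**Conclusion.** The discrepancy is real and follows from the text alone. SAP 4.1.2.1 extends to rescue and therapy increase an exemption that protocol 3.1 and SAP 1.2.1 give only to discontinuation and that protocol 8.4.1 gives to no event. The departure is undeclared, reaches key secondary endpoints 2 and 4, and is not covered by any planned analysis. For endpoint 4 it is also unclear whether the exemption refers to the 4-of-6 or the 6-of-8 response.

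The size is probably a few patients at most, all with events from about week 22 onward. The number cannot be derived from the documents, and the p-values and power figures rest on assumed rates. It should still be fixed before unblinding, because it defines who counts as a responder in the gatekeeping test and one patient could decide a close result.

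**What to change.** In SAP 4.1.2.1, confine the exemption for a response already achieved to discontinuation for lack of efficacy or an adverse event. Classify rescue, or an increase or start of concurrent ITP therapy, at week 12 or later as non-response without exception.

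Align protocol 8.4.1 with protocol 3.1 on discontinuation. The synopsis, protocol 3.1 and 4.2, and SAP 1.2.1 and 4.1.2.1 all carry that exemption, and only 8.4.1 omits it. Use one wording for its timing: protocol 3.1 refers to response within weeks 19 to 24, the SAP to response before the event.

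Apply the same rule to key secondary endpoints 2 and 4, and for endpoint 4 name the response definition meant. If the sponsor does intend the broader exemption, it should be listed and justified in SAP 6.1 and the protocol sections reconciled with it.

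The cost is SAP wording, one derivation flag and a wording correction in protocol 8.4.1. A few patients at most would lose responder status, so the observed response rate may be slightly lower. No patient's care changes.
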